Duration (in days) will be calculated by the difference between the start and stop date + 1 (e.g. duration of a medication (days) = end of medication date – onset of medication date + 1).

Type I error rate

Unless stated otherwise, statistical tests will be two-sided and will be carried out at the 5% level of significance.

7. Description of study subjects

7.1. Definition of analysis sets

The following analysis sets will be defined:

Included set (IS): all of the subjects included in the study.

Safety set (SS): all participants who have been administered study treatment and who received at least one dose of the study treatment, whether prematurely withdrawn from the study or not, will be included in the safety analysis.

Pharmacokinetic set (PKS): all participants who have received at least one dose of study treatment and who have data from at least one post-dose sample will be included in the PK analysis population. Participants will be excluded from the PK analysis population if they significantly violate the inclusion or exclusion criteria, deviate significantly from the protocol, or if data are unavailable or incomplete which may influence the PK analysis. Excluded cases will be documented together with the reason for exclusion. All decisions on exclusions from the analysis will be made prior to database closure.

The analysis sets will be precisely defined and validated during the data review meeting.

The safety and pharmacokinetic sets will be analysed using subjects as treated.

7.2. Subject disposition

A summary table with the description of the number of included subjects, the number of subjects who completed the study and the number of subjects who discontinued the study, classified by main reason of withdrawal, will be prepared overall for the subjects in the included set. Corresponding individual listings will be provided.

A summary table with the description of the number and percentage of subjects in each analysis set (Safety set and Pharmacokinetic Set) will be prepared overall. A specific listing of subjects excluded from safety and pharmacokinetic analyses will be provided with the reason(s) for exclusion.

Listings with end of study status and study visit dates will also be generated.

7.3. Protocol deviations

A summary table with the number and percentage of subjects presenting deviations relating to inclusion/exclusion criteria will be prepared overall for the subjects in the included set. A summary table with the number and percentage of subjects presenting other protocol deviations (all deviations judged relevant during the data review meeting) will also be

prepared overall by status of the deviations (minor/major). The corresponding listings will be provided with the status of the deviations.

8. Demographic data and baseline characteristics

The analyses of the demographic and baseline characteristics will be performed on the safety set.

8.1. Demographic data

The subjects' demographic characteristics (age, sex, ethnicity, height, weight and body mass index (BMI) recorded at screening) will be summarised overall, and listed.

8.2. Other baseline characteristics

Abnormal or positive results as well as all individual data for coagulation, immunology, serum/urine pregnancy tests (for females only) will be listed.

Childbearing potential (for females only) and birth control method (for males only) as well as results for hormonology (for post-menopausal women only) and clinical genotyping will only be listed.

8.3. Medical and surgical history and procedures

Information on medical and surgical history recorded at the screening visit and procedures will be coded according to the Medical Dictionary for Regulatory Activities (MedDRA) Version 21.1.

A table with the number and percentage of subjects having at least one previous/ongoing medical history or one surgical history will be generated overall. Previous/ongoing medical history will be listed as well as prior surgeries and concomitant surgeries.

8.4. Previous and concomitant medications

Information on previous and concomitant medications will be coded according to the GNE Drug Thesaurus.

A previous medication will be defined as a medication stopped prior to the date and time of the first administration of IMP. A concomitant medication will be defined as a medication that is taken by subjects any time during the treatment period (on or after the date and time of first IMP administration for each subject). If the date value does not allow allocation of a medication to the previous or concomitant category (missing or incomplete start or end date), this medication will be considered concomitant.

A table with the number and percentage of subjects having taken at least one previous medication and a table with the number and percentage of subjects having taken at least one concomitant medication will be generated overall (overall and by medication class and medication drug name). Previous and concomitant medications will be listed separately.

8.5. Compliance

A listing with IMP administration dates and times will be generated. Time of meals intake will also be listed.

9. Pharmacokinetic data

The pharmacokinetic analysis will be performed on the PKS.

9.1. Generalities

The following rules for **PK parameter calculation** after each administration will be used:

- Actual sampling times will be used for deriving PK parameters.
- If an entire concentration-time profile is below the limit of quantification (BLQ), BLQ values will not be replaced and the profile will be excluded from the PK analysis.
- For plasma concentrations, all BLQ values occurring prior to the first detectable concentration for each administration and negative values will be replaced by "0".
- All BLQ values occurring after the first detectable concentration for each administration and embedded BLQ values (BLQ values between two measurable concentrations) will be treated as missing.
- If a result is BLQ for the pre-dose PK sample, then the result is set to 0, as well as for all other samples being BLQ before the first detectable concentration and occurring before T_{max} . For subsequent time points, the result must be set to missing. Of note, BLQ values that occur between the first detectable concentration and the T_{max} shall be set to missing.
- If the pre-dose concentration is $\leq 5\%$ of the C_{max} value of the corresponding period for a particular subject, that subject's data, without any adjustments, may be included in all pharmacokinetic and statistical analysis. For each period, if the pre-dose value is $> 5\%$ of C_{max} , two analyses will be performed: one with the pre-dose value and the other one with the pre-dose value replaced by 0.

- If there are late positive concentration values following 2 BLQ concentration values in the apparent terminal phase, these values will be evaluated. If these values are considered to be anomalous, they will be set to missing.
- Some conditions for PK parameters have to be fulfilled:
 - 1) the percentage of the extrapolated AUC should not exceed 20% of the AUC_{0-inf} of each individual profile,
 - 2) the elimination rate constant should be determined over a time interval equal to at least $2 \times T_{1/2}$,
 - 3) the determination of λ_z should use only those data points judged to describe the terminal log-linear decline resulting in an adjusted coefficient of determination value $R^2 > 0.7$, and a minimum of 3 data points will be used in calculating λ_z excluding C_{max} .

If these conditions are not fulfilled, the following unreliable PK parameters will not be calculated, will be considered not determined (ND) in the listings and will be excluded from the analysis:

- 1) if extrapolated AUC $> 20\%$: AUC_{ext} , AUC_{0-inf} and CL/F.
- 2) if the time interval used for the determination of the elimination rate constant is inferior to $2 \times T_{1/2}$ or if the adjusted $R^2 < 0.7$: λ_z , $T_{1/2}$, AUC_{ext} , AUC_{0-inf} , R^2 and CL/F.

The following rules for **plasma concentration versus time graphic representation** will be used:

- No graphic representation will be done if all values are BLQ.
- BLQ values occurring prior to the first detectable concentration will be replaced by “0”.
- All BLQ values occurring after the first detectable concentration will be treated as missing.

The following rules for **mean plasma concentration calculation** will be used:

For BLQ concentrations before the first detectable concentration:

- If more than (or equal to) half of the values are either BLQ values replaceable by zero and/or numeric values: statistics will be calculated with the replaceable and numeric values.
- If more than half of the values are BLQ values not replaceable by zero (i.e., subjects for whom all values are BLQ): only the maximum will be presented and the other statistics will be considered BLQ.

For BLQ concentrations after the first detectable concentration:

- If more than (or equal to) half of the values are not BLQ: statistics will be calculated with BLQ values considered missing data.
- If more than half of the values are BLQ: only the maximum will be presented and the other statistics will be considered BLQ.

For **summary statistics for PK parameters**:

- If more than (or equal to) half of the values are not ND and not missing: statistics will be calculated with the available values.
- If more than half of the values are ND or missing: only the minimum, median and maximum of the available numeric values will be presented. All other statistics will not be calculated and will be presented as ND.

All BLQ concentrations and missing data will be labelled as such in the concentration data listings.

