2. INTRODUCTION

2.1 STUDY RATIONALE

RO7017773 is being developed for the treatment of the 2 core domains of Autism Spectrum Disorder (ASD): social communication deficits and repetitive and restrictive behaviors. RO7017773 has the potential to normalize GABAergic signaling in key brain regions implicated in ASD without the side effects of non-specific GABA_A modulators (e.g., benzodiazepines).

The aim of the study is to investigate the effect of multiple oral doses of itraconazole on the pharmacokinetics (PK) of RO7017773.

CYP3A inhibitors are likely to increase the plasma exposure of RO7017773. Itraconazole, a potent and widely used triazole antifungal agent, is a strong CYP3A inhibitor and is commonly used as a prototypical CYP3A inhibitor in drug-drug interaction (DDI) studies.

This study will allow assessing the magnitude of increase in systemic exposure of RO7017773 when co-administered with CYP3A inhibitors like itraconazole.

The rationale for the study design is provided in Section 4.2.

[figure not shown]

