3. OBJECTIVES AND ENDPOINTS

The objectives and corresponding endpoints are provided in [Table 4](#).

Table 4 Objectives and Endpoints

Objectives	Endpoints
Primary	

To investigate the effect of multiple oral doses of itraconazole on the pharmacokinetics (PK) of a single oral dose of RO7017773 in healthy participants.	
RO7017773 concentrations and RO7017773 PK parameters.
Secondary	

To assess the safety and tolerability of a single oral dose of RO7017773 alone and in combination with multiple doses of itraconazole in healthy participants.	
Incidence and severity of AEs.Changes in vital signs, physical findings, ECG parameters, and clinical laboratory results during and after RO7017773 administration alone and in combination with itraconazole.Change in suicide risk (using the Columbia Suicide Severity Rating Scale [C-SSRS]).

To assess the PK of itraconazole following multiple oral doses of itraconazole alone and in combination with a single oral dose of RO7017773 to ensure adequate CYP3A4 inhibition.	
Concentrations and PK parameters for itraconazole and its metabolites.
Exploratory	

To screen for the presence of RO7017773-derived metabolites.To assess the relative abundance and PK parameters of any metabolite as appropriate.To investigate whether genetic variants of drug-metabolizing enzymes (e.g. CYP3A4) can be related to the pharmacokinetic behavior or observations on the safety of RO7017773 in combination with itraconazole.	
PK concentrations of RO7017773-derived metabolites, if appropriate.PK parameters of RO7017773-derived metabolites, if appropriate.Clinical genotyping.

4. **STUDY DESIGN**

4.1 **OVERALL DESIGN**

An overview of the study design is provided in Section [1.2](#).

This is a single-center, non-randomized, open-label, one-sequence, two-period crossover study in healthy male and female participants to investigate the effect of CYP3A inhibition on the PK of RO7017773 using concomitant administration of itraconazole as CYP3A inhibitor.

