2.3. Exploratory objectives

The exploratory objectives are:

- To screen for the presence of RO7017773-derived metabolites.
- To assess the relative abundance and PK parameters of any metabolite as appropriate.
- To investigate whether genetic variants of drug-metabolizing enzymes (e.g. CYP3A4) can be related to the pharmacokinetic behavior or observations on the safety of RO7017773 in combination with itraconazole.

3. Study methodology

This is a single-center, non-randomized, open-label, one-sequence, two-period crossover study in healthy male and female participants:

- In Period 1, participants will be administered a single oral dose of RO7017773 alone in fed state.
- In Period 2, after a wash-out period of 10 days, participants will receive multiple doses of itraconazole in fed state for 9 days and be administered RO7017773 in combination with itraconazole. The

dose for Itraconazole will be 200 mg BID (12 hours apart) on Day 1 and 200 mg QD from Day 2 to Day 9.

[figure not shown]

As individual discontinuation criteria were not met, and the safety and tolerability profile was considered acceptable during the review of safety, tolerability and PK data of Cohort A, the subjects of Cohort B will be dosed with the same dose like Cohort A (RO7017773 [REDACTED]).

The flow chart and the schedule of assessments are available in section 14.1.

4. Sample Size

Fourteen to eighteen participants will be enrolled in order to obtain at least 12 evaluable participants. This sample size has been chosen to ensure that the ratios of the treatment geometric means can be estimated with sufficient precision.

5. Changes to the planned analysis from protocol

Not Applicable

6. Statistical considerations

Demography and safety data will be analysed using SAS® software version 9.4 or higher (SAS institute Inc. Cary NC USA).

Pharmacokinetic data will be analysed using Phoenix® WinNonlin® version 8.1 or higher (Certara USA, Inc., Princeton, NJ) and SAS® software version 9.4 or higher (SAS Institute Inc. Cary NC USA).

Descriptive statistics will be supplied according to the nature of the criteria:

- Quantitative variable: sample size, arithmetic mean, standard deviation (SD), standard error of the mean (SEM), minimum, median and maximum, and quartiles if necessary [with geometric mean, arithmetic and geometric coefficients of variation (CV), and quartiles for PK parameters].

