9.2.2. Plasma pharmacokinetic analysis

Listings with plasma concentrations (including PK blood sampling dates and times) and PK parameters will be provided by treatment group and subject. These listings will be generated for all subjects with an available PK profile (complete or incomplete), including those who are excluded from the PKS.

Plasma concentrations and PK parameters of RO7017773, and Itraconazole and its metabolite (hydroxy-itraconazole) including descriptive statistics will be presented in tables separately for each treatment group.

Individual plasma concentration versus time profiles of RO7017773, and Itraconazole (and metabolite) will be presented graphically on linear and log/linear coordinates for each subject with all treatment groups received by the subject on the same graph.

The graph of arithmetic mean \pm SD over time will be provided for plasma concentration of RO7017773, and Itraconazole (and metabolite) on linear and log/linear coordinates with all treatment groups on the same graph as well as with all analytes on the same graph only for Itraconazole.

The graph of trough concentrations (mean \pm SD) of Itraconazole (and metabolite) on linear coordinates will also be provided.

Scatter plots and box whisker plots will be generated for the comparison of the C_{max} and AUC (AUC_{0-inf} if it can be derived, otherwise truncated as appropriate (AUC_{0-72})) parameters of RO7017773 between the treatment groups.

For the evaluation of the effect of RO7017773 + itraconazole versus RO7017773 alone, the following linear statistical model will be applied to the log-transformed PK variables AUC (AUC_{0-inf} if it can be derived, otherwise truncated as appropriate (AUC_{0-72})) and C_{max} of RO7017773:

$$y_{ij} = \mu + \tau_j + s_i + \varepsilon_{ij} \quad (i = 1, 2, \dots, 12; j = 1, 2)$$

where μ denotes the general mean of the transformed variables, τ_j is the effect of the treatment (RO7017773 + itraconazole versus RO7017773 alone), s_i is the random subject effect and ε_{ij} is the random error (within subject variability). The random subject effect and the random

error are assumed to be independent and normally distributed with zero means and variances σ_s^2 and σ_e^2 respectively.

Least square means with corresponding 90% confidence intervals (90% CIs) will be derived to compare the relative bioavailability of the different treatments.

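### The concentration tables drop late BLQ values as if missing, so at time points where up to half of the values are BLQ the printed median, minimum and mean describe only the higher participants

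*SAP*

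**What the plan says.** SAP Section 9.1 has separate rules for calculating PK parameters, for graphs and for mean plasma concentrations. This point concerns the last of these. Before the first detectable concentration, BLQ values are replaced by zero and stay in the summary. After it, the SAP has one rule for time points where BLQ values are not in the majority: "If more than (or equal to) half of the values are not BLQ: statistics will be calculated with BLQ values considered missing data". As soon as a single further participant tips the balance the other way, a second and much more restrictive rule takes over: "If more than half of the values are BLQ: only the maximum will be presented and the other statistics will be considered BLQ".

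The statistics concerned are set out in SAP Section 6: "Quantitative variable: sample size, arithmetic mean, standard deviation (SD), standard error of the mean (SEM), minimum, median and maximum", with quartiles if necessary. The geometric mean is added there for PK parameters only. Protocol Section 9.4.3.1 likewise asks for mean, SD, CV, median, minimum and maximum of the concentrations.

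SAP Section 9.2.2 says that the concentrations "including descriptive statistics will be presented in tables separately for each treatment group", and that the arithmetic mean ± SD curves are drawn "on linear and log/linear coordinates with all treatment groups on the same graph". Protocol Section 3, Table 4 gives the primary endpoint as "RO7017773 concentrations and RO7017773 PK parameters".

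BLQ values are labelled in the listings. No BLQ count per time point is specified for the summary tables.

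**The concern.** Treating trailing BLQ values as missing is sound for the non-compartmental analysis, where each profile stands alone. It does not carry over to a summary across participants at one time point. There, the participants removed are exactly those with the lowest concentrations, and what remains is a summary of the higher ones under labels that claim to describe everyone.

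The rule also makes the table jump. With 6 of 12 BLQ a numerical median is printed that sits at the upper quartile; with 7 of 12 the printed median becomes BLQ.

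The two treatments are unlikely to be affected equally. Protocol Section 2.1 states that "CYP3A inhibitors are likely to increase the plasma exposure of RO7017773", and Section 4.3 says that itraconazole may prolong the elimination of RO7017773. At the same late time after dosing, more BLQ values are therefore to be expected for RO7017773 alone, so its tail would be raised more on the shared graph. At stake is the accuracy of concentration tables and mean curves that report part of the stated primary endpoint.

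**Working it through.** The documents give no figure for the effect of this rule, so there is none to reproduce.

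**Inputs from the documents.** The rule and its limit of half BLQ are in SAP 9.1. The number of participants is in SAP Section 4: "Fourteen to eighteen participants will be enrolled in order to obtain at least 12 evaluable participants".

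**Inputs assumed.** The readable text gives no LLOQ, half-life or between-participant CV. I assume log-normal concentrations with CV 30 to 60%, and BLQ fractions of 25% and 50%.

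**Step 1: ranks (no distribution needed).** Let b of n values be BLQ, all below every quantifiable value. The kept values have ranks b+1 to n. The printed minimum is rank b+1. The printed median is rank b + (n − b + 1)/2, which estimates percentile b/n + (1 − b/n)/2. For n = 12 the correct median is rank 6.5.

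| BLQ of 12 | Printed minimum | Printed median | Percentile |
|---|---|---|---|
| 0 | rank 1 | rank 6.5 | 50 |
| 3 | rank 4 | 3 + 10/2 = rank 8 | 62.5 |
| 4 | rank 5 | 4 + 9/2 = rank 8.5 | 66.7 |
| 6 | rank 7 | 6 + 7/2 = rank 9.5 | 75 |
| 7 | maximum only | shown as BLQ | – |

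Exactly half BLQ gives the 75th percentile at other sizes too: rank 11 of 14, 12.5 of 16 and 14 of 18.

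**Step 2: size.** With s = √ln(1 + CV²), BLQ fraction p and z = Φ⁻¹(p):

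- mean factor = Φ(s − z)/(1 − p)
- median factor = exp(s·Φ⁻¹((1 + p)/2))

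For CV 30%, s = √ln 1.09 = 0.294; for CV 60%, s = √ln 1.36 = 0.555.

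| | CV 30% | CV 60% |
|---|---|---|
| Mean, p = 0.25 (z = −0.674) | Φ(0.968)/0.75 = 1.11 | Φ(1.229)/0.75 = 1.19 |
| Mean, p = 0.50 (z = 0) | Φ(0.294)/0.5 = 1.23 | Φ(0.555)/0.5 = 1.42 |
| Median, p = 0.25 | exp(0.294 × 0.319) = 1.10 | exp(0.555 × 0.319) = 1.19 |
| Median, p = 0.50 | exp(0.294 × 0.674) = 1.22 | exp(0.555 × 0.674) = 1.45 |

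**Step 3: check at n = 12.** Simulating 200,000 samples of 12 with exactly 6 BLQ gives median ratios of 1.22 and 1.39, and mean ratios of 1.22 and 1.34, at CV 30% and 50%. The formulas give 1.22 and 1.38, and 1.23 and 1.36.

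**Step 4: direction between treatments.** Take one matched late time, half of the RO7017773-alone values BLQ and, as a further assumption, a true ratio of mean concentrations of 2. The ratio of the tabulated means is then 1.63 at CV 30% and 1.54 at CV 50%. This is a ratio of two descriptive means at one time point, not the planned interaction estimate.

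**The case against.** **No planned inference uses this rule.** This stands in full. A reader might infer that the rule hides part of the drug interaction, because concentrations are named in the primary endpoint. The documents do not support that. Protocol 9.4.3.1 makes AUC and Cmax the primary PK variables. Both are derived from individual profiles under the separate parameter rules, and the mixed model in SAP 9.2.2 uses those individual values. The geometric mean ratios and their 90% CIs do not change.

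**Occurrence is unknown.** This also stands. The effect needs some, but at most half, of the values at a time point to be BLQ, and the 75th percentile is reached only at exactly half. The protocol says that elimination may be prolonged, not that it will be. Very late Period 2 samples can be BLQ as well, so the comparison between treatments is a likelihood at matched times. Nor do geometric-mean figures belong here, since that statistic is not planned for concentrations.

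**Safeguards exist.** Above half BLQ only the maximum is shown. The table template in SAP Section 12 prints n under the group N, listings label BLQ values, and individual graphs show each participant's treatments together. These help, but n below N does not separate a BLQ result from a lost sample, and nothing marks the median as conditional.

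**Substituting LLOQ/2 would not clearly be better.** This stands. Under the same assumptions with half BLQ, it puts the arithmetic mean at 0.85 to 0.92 of its true value. At CV 30, 40 and 60% it puts the SD at 1.38, 1.21 and 1.07 times its true value, against 0.80, 0.86 and 0.97 under the SAP rule. On a mean ± SD graph that exchanges one distortion for another, so I do not propose it.

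**Conclusion.** The point holds for the descriptive concentration tables and mean curves. Wherever some but at most half of the values after the first detectable concentration are BLQ, the printed median lies above the 50th percentile, the printed minimum is not the minimum, and the arithmetic mean is too high. The rank results are exact for any distribution with a single LLOQ. The percentage overstatements rest on the log-normal assumption and the assumed CV range. Whether any time point is affected cannot be settled from the readable text; where no value is BLQ there is no effect. If it happens, RO7017773 alone is likely to be affected more than the combination at matched late times. The primary comparison of AUC and Cmax is unaffected. This is a reporting error worth removing, not a threat to the study's conclusion.

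**What to change.** Leave the parameter rules in SAP 9.1 as they are, with trailing BLQ values missing for the non-compartmental analysis. Change only the rule for concentration summaries after the first detectable concentration:

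1. For the minimum and median, and quartiles if shown, keep BLQ values as the lowest ranks and print BLQ where the required rank falls among them. With 12 values, the median is then fully determined by quantifiable values when at most 5 are BLQ. At exactly 6 it falls between a BLQ and a quantifiable value, so the SAP should state how that case is printed.
2. At each time point show the number BLQ separately from the number missing.
3. Where the mean and SD exclude BLQ values, mark the table entry and the graph point as conditional on quantifiable values.

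No imputation is needed. The cost is one SAP paragraph, one programming rule and a footnote. SAP Section 1 has the plan signed before database lock, so the change belongs before that signature. The primary model and its outputs stay the same.
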